## PROTOCOL SYNOPSIS

## Clinical Protocol ATI001-203

Title
A Single-arm, Open-label Study of Ad-RTS-hIL-12 + Veledimex Following First-, Second-, or Third-Line Standard Treatment in Subjects with Locally Advanced or Metastatic Breast Cancer
Protocol Number
ATI001-203
Clinical Phase
Phase Ib/II
Name of Investigational Product(s)
[REDACTED]-human interleukin-12 (Ad-RTS-hIL-12 [INXN-2001]) + Veledimex (INXN-1001) RTS activator ligand
Ad-RTS-hIL-12 + veledimex may also be referred to in the synopsis and protocol as Ad-RTS-hIL-12 immunotherapy.
Research Hypothesis
A single cycle of Ad-RTS-hIL-12 immunotherapy will be safe and well tolerated and may allow subjects with human epidermal growth factor receptor 2-negative (HER2-) advanced metastatic breast cancer to maintain or improve their pre-study response (partial response [PR] or stable disease [SD]) during a 12-week treatment break from standard chemotherapy. Ad-RTS-hIL-12 immunotherapy also will be safe and well tolerated in patients with HER2-positive (HER2+) metastatic breast cancer who are receiving an established anti-HER2 antibody therapy.
Primary Objective

To evaluate the safety and tolerability of one cycle of Ad-RTS-hIL-12 immunotherapy a) following a first-, second-, or third-line standard treatment in HER2-negative (HER2-) subjects, or b) together with a first-, second-, or third-line anti-HER2 antibody therapy in HER2-positive (HER2+) subjects as defined by Section 12.4.2.

Secondary Objectives

To estimate the progression rate at 12 weeks after the start of one cycle of Ad-RTS-hIL-12 immunotherapy

To evaluate the overall response rate (ORR), defined as the rate of complete response (CR) plus the rate of PR at 12 weeks following the start of Ad-RTS-hIL-12 immunotherapy

To evaluate the disease control rate (DCR), defined as the proportion of subjects who have a CR, PR, or SD at 12 weeks following the start of one cycle of Ad-RTS-hIL-12 immunotherapy

To evaluate the number of subjects whose baseline tumor status (SD or PR) improves to PR or better at 12 weeks following the start of Ad-RTS-hIL-12 immunotherapy

To compare radiographic responses by irRC with conventional reporting by RECIST

To explore the impact of treatment on tumor and blood immune biomarkers

Study Design

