For subjects with HER2- disease, the Ad-RTS-hIL-12 immunotherapy is intended to be given as a chemotherapy holiday, for example, to avoid intolerable or undesirable toxicity of the standard therapy. Ad-RTS-hIL-12 immunotherapy must be started within 4 weeks of stopping the pre-study standard chemotherapy.

Subjects with HER2+ disease will receive the Ad-RTS-hIL-12 immunotherapy in conjunction with first-, second-, or third-line anti-HER2 antibody therapy, i.e., subjects may continue anti-HER2-directed antibody therapy during the study period. Anti-HER2 antibody therapy will be administered according to the manufacturer's recommendations. Subjects with HER2+ breast cancer who continue the anti-HER2 antibody therapy need to recover from any anti-HER2 related AE/SAE, i.e., the event must have resolved to Grade 1 or baseline, before starting Ad-RTS-hIL-12 immunotherapy.

The Ad-RTS-hIL-12 immunotherapy cycle is a 21-day cycle comprised of investigational product administration on days 1 through 7 followed by rest on days 8 through 21. On day 1, enrolled subjects will receive the first dose of veledimex followed 3 hours  $\pm$  3 hours later by an intratumoral injection of Ad-RTS-hIL-12. The veledimex will continue to be given once daily on days 2 through 7 (see [Section 5](#) below, for details).

A safety review committee (SRC) will convene after every 5th subject with HER2- disease have completed the Ad-RTS-hIL-12 immunotherapy cycle (i.e., after each subject has completed 21 days on study). The SRC will also convene after the first 5 subjects with HER2+ disease have completed the Ad-RTS-hIL-12 immunotherapy cycle. The SRC will consist of the investigator, medical monitor, and other appropriate Sponsor representatives. The SRC will review all available safety information (AEs/SAEs, laboratory parameter data, ECG etc.). Tolerability will be evaluated separately for subjects with HER2- and HER2+ disease.

The safety evaluation will be based on the occurrence of related, treatment refractory Grade 3 and 4 AEs within 21 days following the start of Ad-RTS-hIL-12 immunotherapy. A post-treatment safety assessment visit will be conducted on Day 21.

The primary endpoint is safety/tolerability, defined as the proportion of patients who are able to complete 12 weeks on study without a Grade 3 or higher toxicity as defined by [Section 12.4.2](#).

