### **5 INVESTIGATIONAL PRODUCT**

The investigational product has two components: [REDACTED]

[REDACTED]-human interleukin-12 (Ad-RTS-hIL-12) and veledimex (RTS activator ligand). Ad-RTS-hIL-12 is a replication-incompetent adenoviral vector containing the hIL-12 gene under the control of the RTS inducible promoter activated in the presence of the activator ligand, veledimex. Veledimex is a small molecule, RTS-specific transcription factor that stabilizes the RTS promoter components and allows transcription of the hIL-12 target gene. Since target gene expression is dependent on the dose and frequency of veledimex administration, the expression of hIL-12 can be modulated (turned on and off) by the optimal veledimex dose and schedule.

[REDACTED].

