#### **6.8 Severity Grading and Management of Local Reactions**

Injection of agents into tissue carries a potential risk of local reactions that may be characterized as intense immunologic reaction at or near the injection site. Local reactions will be graded according to the NCI CTCAE v.4.03 criteria.

As with all signs and symptoms, events should be recorded and graded as AEs according to NCI CTCAE v.4.03 criteria. Study stopping rules will not apply to a specific event if it is clearly unrelated to the Ad-RTS-hIL-12 injection.

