## 10.5 Determination of Causality

The investigator is required to provide an assessment of relationship of AEs and SAEs to the investigational product. A number of factors should be considered in making this assessment including:

- Alternative possible causes of the AE, including the subject's underlying disease or comorbid conditions, other drugs, other host, and environmental factors
- The temporal sequence between the exposure to investigational product and the AE
- Whether the clinical or laboratory manifestations of the AE are consistent with known actions or previously reported toxicity of the investigational product or similar drugs
- Whether the AE resolved or improved with decreasing the dose or stopping the investigational product (i.e., dechallenge); or recurred or worsened with re-exposure to the drug (i.e., rechallenge).

Relationship assessments that indicate “*Not Related*” to investigational product:

- None: The event is related to an etiology other than the investigational product (the alternative etiology must be documented in the study subject's medical record and/or SAE form).
- Unlikely or Remote: The event is unlikely to be related to the investigational product and likely to be related to factors other than investigational product.

Relationship assessments that indicate “*Related*” to investigational product:

- Possible: There is an association between the event and the administration of the investigational product and there is a plausible mechanism for the event to be related to investigational product; but there may also be alternative etiology, such as characteristics of the subject's clinical status or underlying disease.
- Probable: There is an association between the event and the administration of investigational product, a plausible mechanism for the event to be related to the investigational product and the event could not be reasonably explained by known characteristics of the subject's clinical status or an alternative etiology is not apparent.
- Definite: There is an association between the event and the administration of investigational product, a plausible mechanism for the event to be related to the investigational product and causes other than the investigational product have been ruled out and/or the event re-appeared on re-exposure to the investigational product.

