### 12.4.2 *Safety Analyses*

Exposure to investigational product and reasons for discontinuation of study treatment will be tabulated. All treatment-emergent AEs will be coded according to the system organ class and preferred term using the Medical Dictionary for Regulatory Affairs (MedDRA®), and will be tabulated by number and percent of subjects, and according to relationship to the investigational product, severity, and seriousness. ‘Treatment-emergent’ is defined as any AE that occurs during or after administration of the first dose of investigational product through the evaluation period for safety defined above, regardless of relationship to investigational product; or any event that is present at baseline that worsens in intensity or is subsequently considered to be drug related by the investigator.

Deaths, SAEs, and AEs resulting in patient discontinuation will be listed. Laboratory parameters, vital signs, and physical examination data will be summarized by visit. Data listings will be presented by visit.

Toxicity stopping rules ([Jennison and Turnbull, 2000](#); [Ivanova et al, 2005](#)), when applicable, will be determined based on a clinical assessment made by the SRC after a formal evaluation of safety data after every 5 subjects with HER2- disease have completed one cycle of Ad-RTS-hIL-12 immunotherapy. The SRC will review safety data separately for subjects with HER2+ disease to assess toxicity after the first 5 HER2+ subjects complete one cycle of Ad-RTS-hIL-12 immunotherapy.

The first stopping rule is based on related, treatment refractory Grade 3 or 4 adverse events. A rate of 50% is deemed unacceptable, a rate of 25% is deemed acceptable. The boundaries to stop the study are given as follows:

- If 4 of the first 5 patients have related, treatment refractory Grade 3 or 4 AE, stop the study.
- If 6 of the first 10 patients have related, treatment refractory Grade 3 or 4 AE, stop the study.
- If 8 of the first 15 patients have related, treatment refractory Grade 3 or 4 AE, stop the study.

- If 9 of the first 20 patients have related, treatment refractory Grade 3 or 4 AE, stop the study.
- If 11 of the first 25 patients have related, treatment refractory Grade 3 or 4 AE, stop the study.
- If 12 of the first 30 patients have related, treatment refractory Grade 3 or 4 AE, stop the study.
- If 14 of the first 35 patients have related, treatment refractory Grade 3 or 4 AE, stop the study.

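### Section 6.8 exempts events clearly unrelated to the vector injection from the stopping rules, while Section 12.4.2, read with Sections 5 and 10.5, counts events related to either the vector or veledimex

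*Protocol*

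**What the plan says.** Section 6.8, headed as dealing with the grading and management of local reactions, ends with two sentences. The first is "As with all signs and symptoms, events should be recorded and graded as AEs according to NCI CTCAE v.4.03 criteria". The second is "Study stopping rules will not apply to a specific event if it is clearly unrelated to the Ad-RTS-hIL-12 injection". Veledimex is not mentioned.

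Section 12.4.2 defines what the toxicity boundary counts: "The first stopping rule is based on related, treatment refractory Grade 3 or 4 adverse events". Section 3.1 gives the time frame of the safety evaluation: "related, treatment refractory Grade 3 and 4 AEs within 21 days following the start of Ad-RTS-hIL-12 immunotherapy".

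Relatedness is defined in Section 10.5: "The investigator is required to provide an assessment of relationship of AEs and SAEs to the investigational product". Section 5 states "The investigational product has two components" and lists them as the vector and veledimex.

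The synopsis has its own term for the two agents together: "Ad-RTS-hIL-12 + veledimex may also be referred to in the synopsis and protocol as Ad-RTS-hIL-12 immunotherapy".

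**The concern.** Two causality references apply to one boundary. Sections 12.4.2, 10.5 and 5 together refer to the two-component product. Section 6.8 refers to the injection alone. An event can be related to the first and clearly unrelated to the second, and the protocol does not say which section prevails.

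What is at stake is whether such a patient counts when the boundary is applied. At the first look the rule is to stop at 4 of 5. If one of those four patients qualified only through an event exempt under Section 6.8, the count becomes 3 of 5 and the rule is not met. The text should not leave a stopping decision open to two readings.

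**Working it through.** **Comparison of the texts**

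1. *Does the injection mean the combination?* No. The synopsis reserves the term Ad-RTS-hIL-12 immunotherapy for vector plus veledimex, and Section 3.1 uses it for the 21-day evaluation. Section 4.4 also separates the two agents, since it deals with subjects who received veledimex but not the injection.

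2. *Is Section 6.8 limited to local reactions?* Its heading and opening point that way. The exemption itself speaks of the study stopping rules and of a specific event, and it follows a sentence that refers to all signs and symptoms. The narrow reading is possible, but the wording does not require it.

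3. *Can the disputed event occur?* Yes. Section 6.2 has veledimex taken on days 1 to 7, with the first dose 3 hours ± 3 hours before the injection, so an event may begin up to 6 hours before any vector is given. To be in dispute it must also be Grade 3 or 4, treatment refractory, and related to veledimex.

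4. *Do the causality scales match?* No. Section 10.5 asks for one judgement against the product (none, unlikely or remote, possible, probable, definite). Section 6.8 uses another standard, clearly unrelated, against one component.

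**Operating characteristics of the boundary**

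The protocol gives no error rate or power for this boundary, so there is no stated figure to reproduce. The inputs from Section 12.4.2 are an acceptable rate of 25%, an unacceptable rate of 50%, and stopping at 4/5, 6/10, 8/15, 9/20, 11/25, 12/30, 14/35 and 15/40.

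Let P(n, k) be the probability that the study is still running after n patients with k counted. Then P(n+1, k) = (1 − p)·P(n, k) + p·P(n, k−1). At each look, the mass with k at or above the boundary is removed and added to the stopping probability.

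Hand check of the first look at p = 0.50: (5 + 1)/32 = 0.1875, which agrees with the recursion.

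- At p = 0.25, the probability of stopping by 40 patients is 0.105.
- At p = 0.50, cumulative stopping over the eight looks is 0.188, 0.407, 0.559, 0.770, 0.836, 0.917, 0.941 and 0.970. The expected number treated is 16.9.

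Now let f be the share of qualifying patients whose *only* qualifying event is exempt under Section 6.8. The boundary counts patients, so a patient with any other qualifying event still counts. The documents give no value for f, so it is an assumption. The counted rate at a true 50% is 0.50·(1 − f).

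| f (assumed) | Counted rate | Stop by 30 | Stop by 40 | Expected number treated |
|---|---|---|---|---|
| 0 | 0.50 | 0.917 | 0.970 | 16.9 |
| 0.10 | 0.45 | 0.802 | 0.897 | 21.1 |
| 0.20 | 0.40 | 0.623 | 0.743 | 26.1 |
| 0.30 | 0.35 | 0.408 | 0.513 | 31.1 |
| 0.50 | 0.25 | 0.085 | 0.105 | 38.1 |

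The last two rows only complete the range. The calculation assumes independent patients and one sequence of 40. Tolerability is evaluated separately by HER2 status, with up to 8 HER2+ subjects. If all 8 are enrolled, the HER2− sequence has 40 − 8 = 32 patients and its last full look is at 30, so the column for 30 is then the relevant one.

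**The case against.** The strongest reply is that Section 6.8 concerns local reactions. On that view, its reference to all signs and symptoms is only a comparison, and naming the injection is natural for a reaction at the injection site. Section 12.4.6 locates the stopping rules in Sections 12.4.2 and 12.4.3.2. The synopsis, Section 3.1 and Section 12.4.2 all speak of related events with no exception by component. The safety review committee sees all available safety data and makes a clinical assessment. This may well be what was intended, and a careful committee might never apply Section 6.8 more widely. It does not remove the problem, because the exemption is written for the study stopping rules without limitation and no other section narrows it.

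The reply is right about scale. Veledimex acts by switching on the vector's IL-12 gene, so toxicity mediated by IL-12 is hardly clearly unrelated to the injection. What remains is mainly veledimex's own toxicity.

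Several stronger readings are tempting, and the documents do not support them:

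- *That the toxicity boundary is the only quantitative safety brake.* The synopsis describes two stopping rules intended to ensure safety, and the progression rate in Section 12.4.3.2 includes subjects who discontinue because of an AE.
- *That Section 12.4.2 counts every related event.* The event must also be treatment refractory and Grade 3 or 4, so a veledimex-related Grade 4 event does not count on grade and relatedness alone.
- *That subjects never injected would certainly be lost from the boundary.* Section 4.4 keeps them in the safety analysis group but also withdraws them from the study, and it does not say that they enter the boundary count.
- *That committee members would reach opposite decisions.* The text permits this, but nothing shows that it would happen.

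**Conclusion.** The inconsistency is real and is in the current text. For a treatment-refractory Grade 3 or 4 event within 21 days that is attributed to veledimex and clearly not to the injection, Section 12.4.2 with Sections 10.5 and 5 says count it, and Section 6.8 read literally says do not.

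The size of the effect cannot be determined from the protocol. A small share would still matter: at a true rate of 50%, assumed shares of 10% and 20% lower the chance of stopping by 40 patients from 97% to 90% and 74%. These figures illustrate sensitivity and do not estimate what would happen. The real share is probably low.

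This should be fixed because it bears on a stopping decision and is easy to correct. It does not show that the boundary itself is badly set.

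**What to change.** Reconcile Section 6.8 with Sections 10.5 and 12.4.2 so that one causality reference governs the toxicity boundary. Either of two edits would do this:

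- state the exemption in terms of relationship to investigational product (both components) as assessed under Section 10.5, using that section's categories; or
- limit the exemption expressly to local injection-site reactions, if that was the intent.

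The sponsor should say which was meant. The cost is one sentence in the next amendment. The boundaries and the data collected do not change. Under either edit a few more events may count toward the boundary than under the literal wording of Section 6.8.

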#### **6.9 Prophylactic Antipyretic and/or Analgesic Administration**

The use of antipyretics and/or analgesics is allowed as a prophylactic measure. Antipyretics and/or analgesics can be used anytime during study treatment, as indicated and required for patient safety and must be recorded as concomitant medications. Please refer to exclusion criteria for acute clinically significant and/or chronic infections.

NOTE: Since fever and flu-like symptoms (e.g., fever, headache, chills, dehydration, etc.) are commonly experienced following adenoviral vector administration, it is highly recommended that subjects be treated with prophylactic, antipyretic and/or analgesic medication prior to Ad-RTS-hIL-12 injection and during the first week after injection.

Please refer to [Appendix 16.2](#) for the recommended regimen for the prophylactic administration of antipyretics and/or analgesics.

## 7 CONCOMITANT THERAPY

Information on concomitant medications, including all medications, blood products, vitamins, and other supplements, will be collected from the Screening visit through the end of the Initial Follow-up Period (Week 12). Any new anti-cancer therapy that is started prior to confirmation of a radiographic response of PD, should be collected and entered as a concomitant medication.

### 7.1 Permitted Medications

- HER-directed antibody therapies in patients with HER2+ disease
- Subjects may receive standard treatments, including palliative and supportive care for any illness or symptom management during study treatment.
- Anti-pyretics, analgesics, NSAIDs; Antidiarrheal therapy is permitted for investigational product-induced diarrhea.
- Anti-emetics, with the exception of CYP450 3A4 inducers, inhibitors and substrates, are permitted for investigational product-induced nausea and vomiting.

### 7.2 Prohibited Medications

- Any other investigational agent or anticancer therapy (chemotherapy, radiotherapy, including corticosteroids, etc.) while receiving study treatment.

NOTE: Care should be given when prescribing medications that are classified as CYP450 3A4 inducers, inhibitors, or substrates due to potential interactions with the investigational product. In the event that one is prescribed, consultation with the medical monitor is advised. All medications should be recorded in the case report form (CRF) as indicated in the CRF completion guidelines.

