#### **4.2 Exclusion Criteria**

- 1. Metastatic breast cancer patients currently on hormone therapy as first- or second-line are not permitted
- 2. Prior radiation therapy encompassing  $> 25\%$  of bone marrow
- 3. Any congenital or acquired condition leading to compromised ability to generate an immune response, including concomitant immunosuppressive therapy
- 4. Immunosuppressive therapy
  - a. Use of systemic immunosuppressive drugs including corticosteroids (prednisone equivalent  $\geq 10$  mg/day) within 6 weeks
  - b. Requirement for continual immune suppression with immunosuppressive drugs (e.g., subjects with organ allografts)
- 5. Major surgery within 4 weeks of study treatment, or major surgery planned for duration of study participation
- 6. An active, second potentially life-threatening cancer, adequately treated basal cell or squamous cell skin cancer or carcinoma in situ of the cervix, low grade thyroid is permitted
- 7. Presence of brain or subdural metastases, unless local therapy has been completed and corticosteroids have been discontinued for this indication for  $\geq 4$  weeks before starting study treatment:
  - a. Any signs (e.g., radiologic) and/or symptoms of brain metastases must be stable for  $\geq 4$  weeks before starting study treatment
  - b. Radiographic stability should be determined by comparing contrast-enhanced CT or magnetic resonance imaging (MRI) scans at screening to scans obtained by the same method at least 4 weeks earlier

NOTE: Screening for brain lesions is not required for all potential subjects; however, if there are any neurological signs or symptoms consistent with brain metastases, then a brain CT or MRI should be performed as clinically indicated.

- 8. Presence or documented history of any of the following autoimmune conditions:
  - a. Inflammatory bowel disease

- b. Rheumatoid arthritis, systemic progressive sclerosis (scleroderma), systemic lupus erythematosus, autoimmune vasculitis (e.g., Wegener's granulomatosis)
- c. Motor neuropathy considered of autoimmune origin (e.g., Guillain-Barre Syndrome)

9. Presence of meningeal carcinomatosis
10. Use of any medications that induce, inhibit, or are substrates of cytochrome P450 (CYP450) 3A4 within 7 days prior to the first dose of investigational product without consultation of the medical monitor
11. History or evidence of cardiac disease as indicated by any of the following:

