#### **6.4 Modification of Dose Schedule**

Subjects will receive only one cycle of Ad-RTS-hIL-12 immunotherapy. If a dose of veledimex (up to 2 doses) is held for related toxicity, the treatment related AEs must have resolved to Grade 2 or less for dosing to resume. The held doses will not be made up; the patient will complete dosing according to the remaining schedule.

If a patient misses a dose, the patient is allowed to resume dosing at the next scheduled dose, but must complete dosing according to the remaining schedule. The missed dose will not be made up.

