#### **12.4.3           *Efficacy Analyses***

Efficacy will be based on the tumor response at 12 weeks.

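### Section 7.2 bars other anticancer therapy only for an undefined study-treatment period, and the Week 12 endpoints as written would credit responses obtained after such therapy

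*Protocol*

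**What the plan says.** **What is barred.** Section 7.2 prohibits "Any other investigational agent or anticancer therapy (chemotherapy, radiotherapy, including corticosteroids, etc.) while receiving study treatment". Section 7.1 states: "Subjects may receive standard treatments, including palliative and supportive care for any illness or symptom management during study treatment". It also expressly permits HER-directed antibodies in HER2+ disease.

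**How long treatment lasts.** Section 3.1 describes a "21-day cycle comprised of investigational product administration on days 1 through 7 followed by rest on days 8 through 21", and Section 6.4 adds: "Subjects will receive only one cycle of Ad-RTS-hIL-12 immunotherapy". The schedule of procedures labels the Week 6 and Week 12 visits as initial follow-up. Two places suggest a longer period. Section 4.4 lists confirmed progression among the reasons for stopping study treatment early, and Section 12.4.3.2 describes the 12 weeks over which progression is counted as weeks of immunotherapy.

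**When efficacy is read.** Section 12.4.3: "Efficacy will be based on the tumor response at 12 weeks".

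**How other therapy is handled.** Section 7 asks that "Any new anti-cancer therapy that is started prior to confirmation of a radiographic response of PD" be collected as a concomitant medication. Sections 3.1 and 8.4.8 treat a subject who resumes chemotherapy before Week 12 after unequivocal progression as a failure at Week 12. Section 12.4.3.2 counts three kinds of failure: progression, death, and leaving the trial because of an adverse event. Sections 12.4.3.4 and 12.4.3.5 define ORR and DCR by response status at Week 12, with no reference to other therapy.

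**The concern.** The research hypothesis is that one cycle of the product may maintain or improve a prior SD or PR through a 12-week break from chemotherapy. If other antitumour treatment can begin after dosing and before the Week 12 scan, a subject may be stable or responding at Week 12 for a reason unrelated to the product. Nothing in the endpoint definitions would separate that subject from a true success. With one arm, no comparator absorbs the effect.

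Subjects enter already in SD or PR, so DCR depends on not progressing, which other therapy can delay. The progression rate is also the quantity tested by the second stopping rule, so a masked progression could keep the study open when its own rule would have closed it.

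**Working it through.** **1. The period covered, against the time of reading.** Week 12 is nominally Day 12 × 7 = 84.

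| Meaning of study treatment | Days covered | Days left before Week 12 | Share uncovered |
|---|---|---|---|
| Dosing days (Sections 3.1, 6.2) | 7 | 84 − 7 = 77 | 77/84 = 92% |
| The 21-day cycle (Section 3.1) | 21 | 84 − 21 = 63 | 63/84 = 75% |
| The 12 weeks (suggested by 12.4.3.2) | 84 | 0 | 0% |

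Section 4.4 leans towards a longer reading. Scheduled scans first look for progression at Week 6, and confirmation comes at least 4 weeks later, so confirmed progression on those scans could stop treatment early only if treatment ran past the cycle. The single-cycle dosing text leans the other way. The protocol does not settle it.

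**2. How therapy started before Week 12 is counted.**

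| Therapy started before Week 12 | Rule in the protocol |
|---|---|
| Chemotherapy after unequivocal progression | Failure (3.1, 8.4.8) |
| Chemotherapy without unequivocal progression | None; recorded only (7) |
| Radiotherapy or other anticancer therapy | None; recorded only (7) |
| Anti-HER2 antibody in HER2+ disease | Permitted by design (7.1) |

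For the second and third rows, a Week 12 reading of CR, PR or SD satisfies the DCR definition, a reading of CR or PR satisfies the ORR definition, and neither adds an event to the progression rate. Section 9.1.3.3, on previously irradiated areas, concerns measurability at baseline, not a target lesion irradiated on study.

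**3. Size per subject.** Section 12.2 gives a maximum of 40 subjects and a largest exact 95% half-width of 0.16. The Clopper-Pearson interval for 20/40 is 0.338 to 0.662, so the half-width is (0.662 − 0.338)/2 = 0.162 and the plan's figure is reproduced. On 40 subjects, one credited subject who would otherwise have progressed moves DCR by 1/40 = 2.5 points. A subject who would have stayed stable anyway moves it by nothing.

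**4. Effect on the progression stopping rule.** The boundaries in 12.4.3.2 are 5/5, 9/10, 12/15, 15/20, 18/25, 20/30, 23/35 and 26/40. Let dₙ(x) be the probability of x failures among the first n subjects without having stopped. Then dₙ(x) = (1 − p)·dₙ₋₁(x) + p·dₙ₋₁(x − 1). At each look, the mass at or above the boundary is added to the stopping probability and removed. This gives 0.103 at the acceptable rate of 50% and 0.995 at the unacceptable rate of 80%.

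If a share m of progressors is masked, the observed rate is p = 0.80 × (1 − m). The values of m are assumptions; the documents give none.

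| m | Observed rate | P(stop) |
|---|---|---|
| 0 | 80% | 0.995 |
| 10% | 72% | 0.913 |
| 20% | 64% | 0.623 |
| 30% | 56% | 0.266 |
| 37.5% | 50% | 0.103 |

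**The case against.** **The ban may already run to Week 12.** Study treatment is undefined, and Sections 4.4 and 12.4.3.2 can be read as implying a longer period. This stands. A reader might infer that the ban certainly lapses on Day 8 or Day 22, but the documents do not establish that. They establish an undefined term whose two dosing-based readings leave a gap.

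**Other text limits the gap.** Inclusion criterion 5 requires standard treatment, not only chemotherapy, to be interrupted except for anti-HER2 therapy. Chemotherapy resumed for unequivocal progression already counts as failure and so cannot yield a credited response. Both points narrow the gap, but an entry criterion does not say how therapy started later is counted.

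**Sections 7.1 and 7.2 need not conflict.** The specific prohibition in 7.2 plausibly limits the general allowance in 7.1. A reader might call this a contradiction; it is an overlap in wording that should be clarified.

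**Hormone therapy.** Exclusion 1 reads: "Metastatic breast cancer patients currently on hormone therapy as first- or second-line are not permitted". A reader might infer that it was overlooked when third-line subjects were admitted. It counts lines of hormone therapy, whereas the amendment extended lines of chemotherapy, so no oversight is shown. Nor is an endocrine-treated hormone-receptor-positive subject a strong example of a false responder, because those expressly named as eligible are endocrine resistant.

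**This is for the SAP.** Section 12.4.7 promises a formal plan before database lock, and analysis conventions can go there. However, the protocol itself defines these endpoints and applies the progression boundaries during the study, while that plan is due only before lock.

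**The endpoints are secondary.** This is true, and it limits the weight of the point. The progression rate nevertheless also governs stopping.

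**Conclusion.** The point holds in a limited form. The period of the prohibition is not fixed, and on the 7-day or 21-day reading it ends 77 or 63 days before efficacy is read. Whichever reading is right, Section 7 anticipates new anticancer therapy before confirmed progression, and the progression rate, ORR and DCR as defined would credit a Week 12 CR, PR or SD obtained after it, except for chemotherapy resumed after unequivocal progression. Permitted anti-HER2 antibody therapy is not part of the problem.

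The total bias cannot be derived from the documents. The ceiling is 2.5 points of DCR per affected subject in 40, reached only if that subject would otherwise have progressed. A reader might multiply this by a supposed number of affected subjects to claim a large inflation, but the documents give no such number. The fall in stopping probability from 0.995 to 0.623 when one fifth of progressors are masked is likewise an illustration resting on an assumption. This is an inexpensive correction worth making; it does not touch the primary safety endpoint.

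**What to change.** - **Sections 7.1 and 7.2.** Define study treatment, reconcile the period in 7.2 with the 12-week assessment period, and clarify how the palliative-care allowance in 7.1 relates to 7.2. What care is allowed is for the sponsor's clinicians to decide.
- **Section 12.4.3, subjects.** State that a subject who starts non-protocol antitumour therapy (other than the permitted anti-HER2 antibody) before the Week 12 reading is not credited with CR, PR or SD in ORR or DCR, and is counted as failed in the progression rate. Say whether corticosteroids, which 7.2 lists with anticancer therapy, belong to that class for counting.
- **Section 12.4.3, lesions.** State that a target lesion irradiated on study is not evaluable for response from that date.

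**Cost.** The change is wording only. Sample size is unaffected, and concomitant medications are already collected to Week 12. ORR and DCR may be slightly lower, and a few subjects become not evaluable. Counting such subjects as failed also makes the stopping rule somewhat more likely to act. For illustration only, if the true rate were 50% and 12% of non-progressors were counted as failed, the observed rate would be 0.50 + 0.12 × 0.50 = 56%, and the stopping probability would rise from 0.103 to 0.266. The sponsor should accept that knowingly.
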